4. AMENDMENTS AND UPDATES

Amendment Number	Date	Protocol section(s) Changed	Summary of Amendment(s)	Reason
1	13 Dec2021	Responsible Parties	Added the Pfizer and IQVIA study teams	To reflect the complete study team
	13 Dec2021	Abstract	Removed from the protocol	It is a stand-alone document and should not be in the actual protocol. Added to Annex 1
	13 Dec2021	Milestones	Updated the milestones dates and removed the ones not applicable	To reflect the current situation and progress of the study
	13 Dec2021	Study Design	Updated the countries (Egypt, Jordan,, KSA, Lebanon, Morocco, Qatar and UAE) and the number of centers to 19	To reflect the changes in participating countries and the number of centers enrolled.
	13 Dec2021	Study Size (table 3)	Updated the planned number of subjects per centers per country	To reflect the changes in participating countries and the number of centers enrolled.
2	8 November 2022	Study Design	Extension of enrollment period 18 months instead of 12 months	Challenges in patients recruitment due to change of treatment protocols in some countries
	8 November 2022	Study Size (table 3)	Reducing sample size to 200 subjects instead of 340 subjects	Challenges in patients recruitment due to change of treatment protocols in some countries
	8 November 2022	Milestones	Updated the milestones dates	To reflect the current situation and progress of the study and the extension in the enrollment period

090177e19bc3ff14\Approved\Approved On: 10-Nov-2022 09:28 (GMT)

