8. RESEARCH METHODS

8.1. Study Design

This is a prospective, non-interventional (NI), multicenter study being conducted in Africa Middle East (AfME) countries. The aim is to understand palbociclib treatment patterns, clinical outcomes and QoL for patients with metastatic/locally advanced BC being treated in routine clinical practice in 7 AfME countries: Egypt, Jordan, KSA, Lebanon, Morocco, Qatar and UAE.

Approximately 200 patients from 19 centers across the 7 countries will be enrolled. The recruitment period (ie, from first patient into last patient in) will span over 18 months.

[figure not shown]
Patients will be enrolled at the time of treatment initiation with palbociclib and will be followed up over a 24-month period at time intervals per routine care, or until patient's withdrawal from the study or death (whichever comes first). Prospective data on clinical characteristics, treatment patterns, clinical outcomes and QoL will be collected ([Figure 1](#)).

Participation in this study is not intended to change the routine treatment patients receive, as determined by their prescribing physicians; all treatment decisions, type and timing of the disease monitoring are per routine clinical care, and at the discretion of treating physician and patient.

All assessments described in this protocol are performed as part of normal clinical practice or standard practice guidelines for the patient population and healthcare provider specialty in the countries where this non-interventional study is being conducted.

All assessments described in this protocol are performed as part of normal clinical practice or standard practice guidelines for the patient population and healthcare provider specialty in the countries where this non-interventional study is being conducted.

Figure 1. Study Design

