8.5. Study Size

This is an observational study of drug usage without any pre-defined hypothesis to be tested; rather, it addresses descriptive objectives. Sample size calculations were performed per country taking into account population size, estimated MBC prevalence, and a margin of error of 5%. A minimum sample size of 15 patients per country (total sample size of 105 patients) was estimated on this basis.

A planned total sample size of approximately 350-410 patients ([Table 3](#)) will be applied to ensure adequate exploration of the objectives and sufficient generalizability.

Table 3. Planned Number of Subjects and Centers per Country

Country	Estimated Number of Centers	Estimated Number of Subjects
Egypt	5	60
Gulf (UAE/Qatar)	2	20
Jordan	1	20
Lebanon	6	65
Morocco	2	15
KSA	3	20
Total	19	200

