2. INTRODUCTION

Note: in this document, any text taken directly from the non-interventional (NI) study protocol is ***italicised***. The protocol version 2.0, dated in 13 December 2021 was used to develop the SAP.

Breast cancer (BC) is a complex, heterogenous disease encompassing multiple tumor entities with specific pathologic features and biological behaviors.¹ It is the most common neoplasm among women with an estimated incidence of 2.4 million cases and 523,000 deaths in the year 2015.² Approximately 6%-10% of new BC cases are diagnosed as stage IV metastatic disease and an estimated 20%-30% patients with early BC experience relapse with distant metastatic disease.³

Absolute rates of BC incidence are higher in high-income countries (HICs), however incidence rates are also increasing in lower-middle-income countries (LMICs).² The age-standardized rate (ASR) per 100,000 population for BC worldwide is 43.1.⁴ The highest BC incidence rates are in North America, Australia, New Zealand, and Northern and Western Europe.⁵ The incidence rate varies from 19.4 per 100,000 people in East Africa to 89.7 per 100,000 in West Europe.⁶ Mortality rates of BC depend on the availability of early detection and treatment.⁴ Hence, the mortality rates are higher in many LMICs, such as those in sub-Saharan Africa due to their late stage diagnosis and limited access to treatment as compared to HICs.⁵ The 5 year survival rate is 85% or higher in the United States, Canada, Australia, Israel, Brazil, and many Northern and Western European countries, whereas it is 60% or lower in many LMICs, such as South Africa, Mongolia, Algeria, and India.⁵

Breast cancer is one of the most prevalent cancers in the Middle East (ME), where it is also the most common cause of death among females.⁷ The BC cases diagnosed in this geography are more aggressive and associated with worse outcomes compared to cases evidenced in other parts of the world, which may partly be explained by late diagnosis.⁷

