2.1. Study Design

This is a prospective, non-interventional (NI), multicentre study being conducted in Africa Middle East (AfME) countries. The aim is to understand palbociclib treatment patterns, clinical outcomes and QoL of patients with metastatic/locally advanced BC being treated in routine clinical practice in seven AfME countries: Egypt, Jordan, Lebanon, UAE, Qatar, Morocco and KSA.

Participation in this study is not intended to change the routine treatment patients receive, as determined by their prescribing physicians; all treatment decisions, type and timing of the disease monitoring are per routine clinical care, and at the discretion of the treating physician and patient.

Study population

[figure not shown]
Patients with HR+/HER2- metastatic/locally advanced BC within Egypt, Jordan, Lebanon, UAE, Qatar, Morocco and KSA will be enrolled from a geographically representative population as well as from diverse treatment settings (eg, academic and community sites). Patients whose treatment decision with palbociclib combination has been made by their treating physician and meet the eligibility criteria will be invited to participate in the study in a consecutive manner and over 12 months of recruitment.

Approximately 350-410 patients from 19 centers across the seven countries will be enrolled. The recruitment period (ie, from first patient in to last patient in) will span over 12 months.

Patients will be enrolled at the time of treatment initiation with palbociclib, and will be followed up over a maximum of 24-month period at time intervals per routine care, or until the end of Palbociclib treatment, progression or patients' withdrawal from the study (whichever comes first). Eligibility will be assessed at the date of the enrollment.

Prospective data on clinical characteristics, treatments patterns, clinical outcomes and QoL will be collected in accordance with routine standard of care visits (Figure 1). Data will be collected at enrollment (time of treatment initiation), during treatment with Palbociclib (at time intervals per routine care) and after treatment with palbociclib. After the end of treatment with palbociclib, data related to the first immediate subsequent treatment received will be collected.

Figure 1. Study Design

FPI: first patient in; LPI: last patient in; LPO: last patient out; QoL: quality of life

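### Protocol 8.5 and SAP 2.1 still state 350-410 patients while Table 3 and Protocol 8.1 plan 200, so the adequacy statement is attached to a size that will not be enrolled

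*Protocol*

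**What the plan says.** Protocol 8.5 (Study Size) makes two statements about size.

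- The first is a calculated minimum: "A minimum sample size of 15 patients per country (total sample size of 105 patients) was estimated on this basis". It was worked out per country, "taking into account population size, estimated MBC prevalence, and a margin of error of 5"%.
- The second is the planned total: "A planned total sample size of approximately 350-410 patients", with Table 3 cited for it, which "will be applied to ensure adequate exploration of the objectives and sufficient generalizability".

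Table 3, printed directly below, lists 19 centers and 200 subjects. Protocol 8.1 (Study Design) agrees with the table: "Approximately 200 patients from 19 centers across the 7 countries will be enrolled".

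SAP 2.1 has the larger figure: "Approximately 350-410 patients from 19 centers across the seven countries will be enrolled". SAP section 2 explains where it came from: "The protocol version 2.0, dated in 13 December 2021 was used to develop the SAP". The current protocol is version 3.0 of 8 November 2022.

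For context only, the entry for Amendment 2 in Protocol section 4 reads "Reducing sample size to 200 subjects instead of 340 subjects". It shows which figure is intended. The finding does not depend on it.

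**The concern.** Two sample sizes that differ by 150 to 210 patients stand together in operative text: within Protocol 8.5, between 8.5 and 8.1, and between the current protocol and the SAP. The larger one carries the only statement in 8.5 that the study is big enough for its objectives and can be generalized. If enrolment goes to plan, that statement will have been made about a study that was not run.

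A reader also cannot settle the SAP conflict by assuming that the protocol prevails, because Protocol 8.7 allows the SAP to depart from the protocol's plans. What is at stake is the accuracy of a core design figure and of the claim built on it. A final report that repeats 8.5 would overstate the planned size and leave the adequacy of 200 unexplained.

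**Working it through.** **Inputs**
- Subjects by row of Table 3 (Protocol 8.5): Egypt 60, Gulf (UAE/Qatar) 20, Jordan 20, Lebanon 65, Morocco 15, KSA 20.
- Centers in the same order: 5, 2, 1, 6, 2, 3.
- Stated total: 350-410 (Protocol 8.5, SAP 2.1).
- Stated minimum: 15 per country, 7 countries (Protocol 8.5).
- For illustration, two progression-free rates from Protocol 6.1, both from a US chart review of first-line palbociclib plus letrozole: 51.6% at 18 months and 75.5% at 12 months.

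**Step 1. Reproduce the plan's own figures**
- Minimum: 15 × 7 = 105. Reproduces.
- Table 3 subjects: 60 + 20 + 20 + 65 + 15 + 20 = 200. Reproduces the table's total and the figure in 8.1.
- Table 3 centers: 5 + 2 + 1 + 6 + 2 + 3 = 19. Reproduces.
- Planned total of 350-410: does not reproduce from Table 3, the table cited for it. No calculation in either document yields it.

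**Step 2. Size of the discrepancy**
- Difference: 350 − 200 = 150; 410 − 200 = 210.
- Stated over planned: 350/200 = 1.75; 410/200 = 2.05.
- Planned over stated: 200/350 = 57%; 200/410 = 49%.

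**Step 3. Illustrative precision**

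The 95% Wald half-width for a single proportion is 1.96 × √(p(1 − p)/n). The 95% level is assumed here for Protocol 8.5, which gives no confidence level.

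| p | n = 200 | n = 350 | n = 410 |
|---|---|---|---|
| 0.516 | 6.9 points | 5.2 points | 4.8 points |
| 0.755 | 6.0 points | 4.5 points | 4.2 points |

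For example, 1.96 × √(0.516 × 0.484/200) = 0.069. The ratio of half-widths does not depend on p: √(350/200) = 1.32 and √(410/200) = 1.43.

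**Step 4. Is 350-410 a documented precision target?**

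A 5-point margin at p = 0.5 needs 1.96² × 0.25/0.05² = 384.2, rounded up to 385, which lies inside 350-410. But the documents attach the 5% margin to the per-country minimum only. With the same formula (95% level, no finite-population correction), a minimum of 15 requires a proportion of about 1%: 1.96² × 0.00986 × 0.99014/0.05² = 15.0. That is far from the outcome proportions in the table above. The agreement with 385 is an inference, not a stated derivation.

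**The case against.** The strongest reply is that the operative number is not seriously in doubt. Protocol 8.1, every row of Table 3 and Amendment 2 point to 200, so one lead-in sentence was left unrevised above a corrected table. The SAP figure is version lag that the SAP itself discloses. Its approval record shows version 1 of February 2022, about nine months before protocol version 3.0, and it also still has 12 months of recruitment where the protocol now has 18. No estimator, analysis set or censoring rule uses the planned size. All of this stands. It settles which figure is right and limits the consequence, but the sentence in 8.5 remains wrong and the SAP still needs updating.

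A reader might infer more than the documents support:

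- **Lost power, or a sample that is too small.** Protocol 8.5 and 8.7 describe a study with no hypothesis and no testing. There is no alpha, power or event target to miss, and the only calculated requirement is the minimum total of 105.
- **A missed 5-point precision target.** Step 4 shows why this is tempting, but neither document sets a precision target for the total.
- **Stratified tables that must be cut.** Protocol 8.7 and SAP 3.2 already make stratification depend on having enough patients, SAP 3.2 warns that some strata may not be meaningful, and SAP 6.1 names combination therapy and line of therapy as the minimum for the primary outcomes. Nothing shows that the table shells were derived from 350-410. Nor is every objective stratified seven ways: the demographic and baseline clinical tables are split by line only.
- **The SAP as independent support for a larger plan.** It is the same figure carried over from an earlier protocol version.

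**Conclusion.** The planned total in Protocol 8.5 is wrong as written. It is 1.75 to 2.05 times the enrolment planned in the table it cites and in 8.1, and SAP 2.1 carries the same outdated figure. The adequacy and generalizability statement therefore has no support at the size that will be enrolled.

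The discrepancy of 150 to 210 patients rests on addition alone. The precision comparison, with half-widths about 1.3 to 1.4 times wider at 200, is illustrative. It assumes a 95% level, a simple proportion and no censoring, whereas SAP 6.1 specifies Kaplan-Meier for progression-free proportions. It also borrows rates from a first-line US population, while this study also takes second-line and fulvestrant patients.

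The comparison with 105 concerns totals only. How the combined UAE/Qatar row of 20 relates to a minimum of 15 for each country is a separate question and is not part of this point.

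**What to change.** 1. In Protocol 8.5, replace 350-410 by 200, so that the sentence agrees with Table 3 and with 8.1.
2. In the same place, either delete the statement on adequacy and generalizability, or restate it as expected precision. A usable form would be that, with 200 patients and before any loss to censoring, a proportion near 0.5 is estimated with a 95% half-width of about 6.9 percentage points.
3. In SAP 2.1, replace 350-410 by 200 and update the statement of which protocol version the SAP follows.

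No analysis, table shell or stratification rule has to change. The cost is wording in two documents, and the stated size and precision become less favourable than the present text suggests.

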8.6. Data Management

8.6.1. Case Report Forms (CRFs)/Data Collection Tools (DCTs)/Electronic Data Record

As used in this protocol, the term CRF should be understood to refer to either a paper form or an electronic data record or both, depending on the data collection method used in this study.

An eCRF is required and should be completed for each included patient. The completed original eCRFs are the sole property of Pfizer and should not be made available in any form to third parties, except for authorized representatives of Pfizer or appropriate regulatory authorities, without written permission from Pfizer. The investigator shall ensure that the eCRFs are securely stored at the study site in encrypted electronic *and/or paper* form and will be password protected *or secured in a locked room* to prevent access by unauthorized third parties.

The investigator has ultimate responsibility for the collection and reporting of all clinical, safety, and laboratory data entered in the eCRFs and any other data collection forms (source documents) and ensuring that they are accurate, authentic/original, attributable, complete, consistent, legible, timely (contemporaneous), enduring, and available when required. The eCRFs must be signed by the investigator or by an authorized staff member to attest that the data contained on the eCRFs are true. Any corrections to entries made in the eCRFs or source documents must be dated, initialed, and explained (if necessary) and should not obscure the original entry.

In most cases the source documents are the hospital or the physician's chart. In these cases, data collected on the CRFs/[DCTs] must match those charts.

In some cases, the CRF/[DCT] may also serve as the source document. In these cases, a document should be available at the investigator site and at Pfizer that clearly identifies those data that will be recorded on the CRF/[DCT], and for which the CRF/[DCT] will stand as the source document.

8.6.2. Record Retention

To enable evaluations and/or inspections/audits from regulatory authorities or Pfizer, the investigator agrees to keep records, including the identity of all participating patients (sufficient information to link records, eg, CRFs and hospital records), all original signed informed consent documents, copies of all CRFs, safety reporting forms, source documents, detailed records of treatment disposition, and adequate documentation of relevant correspondence (eg, letters, meeting minutes, and telephone call reports). The records should be retained by the investigator according to local regulations or as specified in the clinical study agreement (CSA), whichever is longer. The investigator must ensure that the records continue to be stored securely for as long as they are retained.

If the investigator is unable for any reason to continue to retain study records for the required period (eg, retirement, relocation), Pfizer should be prospectively notified. The study records must be transferred to a designee acceptable to Pfizer, such as another investigator, another institution, or to an independent third party arranged by Pfizer.

Investigator records must be kept for a minimum of 15 years after completion or discontinuation of the study or as required by applicable local regulations.

The investigator must obtain Pfizer's written permission before disposing of any records, even if retention requirements have been met.

8.7. Data Analysis

Detailed methodology for summary and statistical analyses of data collected in this study will be documented in a statistical analysis plan (SAP), which will be dated, filed and maintained by the sponsor. The SAP may modify the plans outlined in the protocol; any major modifications of primary endpoint definitions or their analyses would be reflected in a protocol amendment.

This is a descriptive study, and as such, no statistical testing will be conducted. Analyses will be conducted using Statistical Analysis System (SAS) (version 9.3 or higher). Summary statistics for patient demographics, clinical characteristics, treatment patterns and QoL will be performed. Summary statistics for continuous variables will include number of observations, mean, standard deviation, median, 1st and 3rd quartiles, minimum, and maximum. Summary statistics for categorical data will include number of observations, counts and percentages. Kaplan-Meier analyses will be performed on time-to-event outcomes, eg, TTP, response and death.

Exploratory stratifications will be conducted (where adequate numbers of patients permit) to explore differences by eg, country, line of therapy, menopausal status, de novo versus recurrent disease, age (<55 years vs. ≥55 years), and combination therapy (ie, palbociclib plus letrozole/aromatase inhibitor vs. palbociclib plus fulvestrant). The data may also be evaluated and presented by other meaningful subgroups, as outlined in the SAP.

Should missing data occur, the data will be analyzed as they are recorded in the eCRFs, and no imputation of missing data will be performed. The amount of missing values for data elements will be reported.

8.8. Quality Control

Investigators will be trained with an initial on-site visit to the clinic on the protocol, electronic data capture (EDC) system (ie, eCRF), investigator site master file (ISMF), documentation, and any applicable study processes. Any new information relevant to the performance of this non-interventional study (NIS) will be forwarded to the medical staff during the study. Remote data monitoring will be conducted during the life of the study to ensure timely reporting of safety data, data integrity and consistency. The eCRFs for all included patients will be made available to the remote data monitor for review. A list of critical variables will be created as required elements for review during the remote data monitoring process. The study sites will be queried and managed to request resolution to any issues that may arise during the course of the study.

Monitoring visits may be made, if necessary, to monitor study process by Pfizer, Inc. or its delegate. In the event of a visit, direct access to original source data will be required for monitoring visits and/or inspections/audits, which will be carried out with due consideration for data protection and patient confidentiality.

Items routinely checked during on-site visits include:

- Documentation of the informed consent process.
- Compliance with patient eligibility criteria.
- Proper maintenance of records, such as study protocol.
- Completed eCRFs.
- Documentation of AEs, and transmission of serious adverse events (SAEs).
- Identification of patients lost to follow-up.
- Study correspondence.
- Compliance with Institutional review board (IRB)/ Independent ethics committee (IEC) approval requirements.
- Review of the ISMF.
- Archiving of the study documents will be performed accordingly to Pfizer standard operating procedures (SOPs).

8.9. Limitations of the Research Methods

A key limitation of a study of this nature is the reliance on accurate, complete CRFs, which is dependent on the correct completion of the CRFs and the availability of detailed, complete patient records. We have outlined a number of important quality control steps to be taken as part of the study procedures to minimize the impact of this. Notably, to reduce the administrative burden on all physicians, only data elements that are relevant for addressing the research objectives will be collected.

As this is a NIS, potential bias cannot be ruled out. Data collection will reflect routine clinical practice rather than mandatory assessments at prespecified time points, which may have an impact on the amount of data available and its interpretation.

